
	1. change in Everyday Cognition (score range: 1 to 4)		
	2. change in Geriatric Depression Scale score (score range: 0 to		
	15)		
	3. change in Pittsburgh Sleep Quality Index global score (score		
	range: 0 to 21)		
	4. change in EuroQol EQ-D5 utility score (score range: -1 to 1)		
Covariates	There are no pre-specified covariates for the primary and secondary		
	endpoints.		
Follow-up schedule	16 weeks (mid point), 24 weeks (intervention termination), 48 weeks		
,	(post-intervention follow-up)		
Masking	Outcome assessors, data analysts		
Number of subjects	The target sample size is 315 participants to provide 80% power to		
3	detect a medium-size difference in mean MoCA change of 1.5 points		
	between the cognitively enhanced tai ji quan and the standard tai ji		
	quan groups and a large-size difference of 3 points between the		
	cognitively enhanced tai ji quan and the stretching control groups at 24		
	weeks.		
Statistical analysis	The effect of the intervention on the primary endpoints will be		
	evaluated using the intention-to-treat approach, in which participants		
	are grouped according to randomization assignment. To compare		
	change in outcome measures among the three intervention groups at 6		
	months, we will analyze a 3 (Group) by 3 (Time) mixed-effects model		
	with repeated measures on the second factor (i.e., outcome measures		
	assessed at baseline, 4 months, and 6 months). In the presence of a		
	Group by Time interaction effect, pre-specified follow-up pair-wise		
	comparisons will be performed to determine between-group		
	differences (indicated below). Secondary outcomes will be similarly		
	analyzed. Results from primary analyses will be presented as the		
	difference in mean MoCA and dual-task performance between the		
	cognitively enhanced tai ji quan and standard tai ji quan groups and		
	between the cognitively enhanced tai ji quan and the stretching		
	exercise control, with a Bonferroni-adjusted 2-tailed significance level		
	of .0125 for each of the two primary outcomes and a 98.75%		
Intonia analysis	confidence interval.		
Interim analysis	No interim analyses for efficacy or futility. However, interim		
	monitoring is performed with a focus on subject accrual, intervention		
	fidelity, protocol adherence, data completeness and quality, and		
	intervention safety and analysis.		

Study Background and Rationale

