In the presence of a Group by Time interaction effect, follow-up pair-wise comparisons, using independent t tests, will be performed to identify a priori specified between-group differences. Specifically, we will determine the intervention effect of cognitively enhanced tai ji quan for change in MoCA and costs of dual task in gait performance from baseline to 24 weeks by making a comparison between cognitively enhanced tai ji quan and standard tai ji quan and between cognitively enhanced tai ji quan and stretching exercise.

Level of statistical significance and confidence intervals. Our primary outcome analyses will be 2-sided with an adjusted significance level of <0.0125 (0.05 / 4 comparisons) and a 98.75% confidence interval (CI). For each group, both estimated means and their corresponding standard error of estimates at each assessment point will be presented. In presenting between-group differences, mean differences with CIs will be presented. SPSS "MIXED" function will be used in analyzing our primary outcomes.

Secondary and tertiary outcome analyses

A similar analytic approach will also be applied to all secondary and tertiary (continuous) outcome variables described in Table 1. All study outcomes are expected to follow a normal distribution. In the case of deviation from normality, generalized estimating equations will be used to assess the effect of intervention over time. No Bonferroni correction will be made to account for multiple comparisons.

Level of statistical significance and confidence intervals. All tests and CIs will be 2-sided, and statistical significance will be defined as a P value of <0.05. For each group, we will report both estimated means and their corresponding standard error of estimates at each assessment point. In presenting between-group differences at 24 weeks, estimated mean differences with CIs will be presented.

Analyses on examining intervention durability at 48-week follow-up

We will use the same analytic strategy outlined in our primary and secondary outcome analyses, with the exception of CDR-SB (described in detail below), to examine whether the intervention effects will persist 24 weeks after the end of the 24-week supervised interventions (*Secondary hypothesis*).

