Note: Group is a binary variable involving a comparison between cognitively enhanced tai ji quan and standard tai ji quan or cognitively enhanced tai ji quan and stretching exercise.

Post-hoc exploratory analyses

No pre-specified post-hoc exploratory analyses are planned.

Subgroup analyses

In light of the findings reported in prior studies, 36,37 we also plan to conduct a series of subgroup analyses. Specifically, using a three-way interaction model that involves factors of Group, Time, and Subgroup, we will examine whether the expected between-group differences in the two primary outcomes are associated with pre-specified subgroups that include sex (1 = men, 2 = women), age (1 = 65-74, 2 = 75-84, 3 = 85+ years old), and level of education (1 = high school diploma or lower, 2 = college degree or higher). We are aware of the fact that these subgroup analyses are not powered statistically, and we will therefore interpret any statistically significant results with caution. All subgroup analyses are based on an alpha level of <0.05.

Power estimation for primary outcomes

This study is powered to detect a mean difference in change in the primary outcomes of MoCA and motor-cognitive dual-task gait performance between (a) the cognitively enhanced tai ji quan intervention and a standard tai ji quan intervention operationalized by TJQMBB, ¹⁰ and (b) the cognitively enhanced tai ji quan intervention and a non-tai ji quan control condition – stretching – at 6 months, among older adults with MCI. We estimated the magnitude of the effect size (difference score divided by its pooled standard deviation) that is detectable with at least 80% power using a 2-sided 0.05-level test. We expect that participants in the cognitively enhanced tai ji quan intervention would experience a clinically meaningful improvement of at least 1 score unit in MoCA and a 10% reduction in dual-task costs on gait performance speed between the enhanced tai ji quan intervention and each of the two comparison arms. The following details the parameters used and results of our power analyses for each of the two primary outcomes.

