Efficacy analyses. The effect of intervention on the co-primary study outcomes will be evaluated using an intention-to-treat approach in which participants will be analyzed according to randomization assignment. A modified intention-to-treat analysis will be conducted that includes all participants who have undergone randomization and have completed all study follow-up assessments, regardless of their participation adherence status. Finally, a per-protocol analysis will include participants in the intention-to-treat population who have an overall class attendance rate of $\geq 75\%$ (out of the total planned 48 intervention class sessions) of their assigned exercise intervention.¹⁰

Co-primary endpoint analyses

To test the *Primary hypothesis*, we plan to use a generalized linear mixed model with random intercepts and fixed treatment effects for the primary outcomes. Specifically, we will determine the intervention effect through an analysis of a 3 (Group) by 3 (Time) mixed-effects model with repeated measures (follow-up time point) on the second factor (i.e., outcome measures assessed at baseline, 4 months [mid-point], and 6 months [intervention termination]).

In the presence of a Group by Time interaction effect, follow-up pair-wise comparisons, using independent t tests, will be performed to identify a priori specified between-group differences. Specifically, we will determine the intervention effect of cognitively enhanced tai ji quan for change in MoCA and costs of dual task in gait performance from baseline to 24 weeks by making a comparison between cognitively enhanced tai ji quan and standard tai ji quan and between cognitively enhanced tai ji quan and stretching exercise.

Level of statistical significance and confidence intervals. Our primary outcome analyses will be 2-sided with an adjusted significance level of <0.0125 ($0.05 / 4$ comparisons) and a 98.75% confidence interval (CI). For each group, both estimated means and their corresponding standard error of estimates at each assessment point will be presented. In presenting between-group differences, mean differences with CIs will be presented. SPSS “MIXED” function will be used in analyzing our primary outcomes.

Secondary and tertiary outcome analyses

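### The four primary contrasts are each tested by single-step Bonferroni at 0.0125; Holm's procedure keeps the same 5% family-wise error and would add about 4 to 15 points of power for enhanced versus standard tai ji quan on MoCA

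*Protocol*

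**What the plan says.** For each primary outcome, the section on co-primary endpoint analyses (the same text in the Protocol and the SAP) compares change "between cognitively enhanced tai ji quan and standard tai ji quan and between cognitively enhanced tai ji quan and stretching exercise". Two outcomes and two comparators make four contrasts.

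The paragraph there on significance level sets an "adjusted significance level of <0.0125 (0.05 / 4 comparisons) and a 98.75% confidence interval (CI"). The standalone SAP has the same rule: "2-sided with an adjusted significance level of <0.0125". The Protocol Synopsis, under Statistical analysis, also gives .0125, "with a Bonferroni-adjusted 2-tailed significance level". All three places agree. None describes a step-down, hierarchical or alpha-recycling rule.

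A gate comes before the contrasts: "In the presence of a Group by Time interaction effect, follow-up pair-wise comparisons, using independent t tests, will be performed".

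The section on power estimation plans MoCA differences of 1.5 points against standard tai ji quan and 3 points against stretching, with SD 3.5, 267 evaluable participants and a correlation of 0.7. For dual-task cost it gives reductions of 10% and 20% but no SD.

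**The concern.** Single-step Bonferroni reserves a quarter of the 5% for each contrast and never releases it. The plan expects the stretching contrast on MoCA to be twice as large as the standard tai ji quan contrast, so its rejection is almost certain. Once it is rejected, its share of alpha protects nothing, yet the remaining contrasts are still held at 0.0125.

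The contrast that loses most is enhanced versus standard. It has the smaller planned effect and is the one that isolates what the added cognitive tasks contribute. What is at stake is efficiency: a lower chance of confirming a true effect there, with no compensating gain in family-wise error control.

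**Working it through.** **Inputs** (power estimation section unless noted)
- Evaluable participants: 267, so 267/3 = 89 per arm under 1:1:1 allocation.
- MoCA differences: 1.5 points (versus standard) and 3 points (versus stretching); SD 3.5.
- Level per contrast: 0.05/4 = 0.0125, two-sided.
- Assumed, because no dual-task SD is given: standardized dual-task effects equal to MoCA's, half of them, or zero. Correlation between the two outcomes: 0 to 0.6 (0 to 0.5 for power on all four contrasts and for the interval figures).
- The two contrasts within an outcome correlate 0.5, because they share the enhanced arm and the arms are equal in size.

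**The plan's own figure.** Normal approximation: power = Φ(δ / (SD·√(2/n)) − z).
- δ/SE = 1.5 / (3.5 × √(2/89)) = 1.5/0.525 = 2.86.
- At 0.05: Φ(2.86 − 1.96) = 81.6% (non-central t 81.2%). This reproduces the stated power above 80%, with 3.5 read as the SD of change.

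**The same contrast at other levels:** 73.2% at 0.025, 67.9% at 0.0167, 64.1% at 0.0125 (63% by non-central t). The 3-point contrast has 99.9% power at 0.0125.

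**Holm's rule.** Order the four p-values and compare them with 0.05/4 = 0.0125, 0.05/3 = 0.0167, 0.05/2 = 0.025 and 0.05. Stop at the first failure. Since 0.0125 is the smallest threshold, every Bonferroni rejection is also a Holm rejection.

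**Hand check, equal standardized effects, independent outcomes.** Both stretching contrasts are nearly always rejected. The two enhanced-versus-standard contrasts are then tested with the smaller p-value at 0.025 and the other at 0.05. Power for MoCA is 0.732 + (0.816 − 0.732) × 0.732 = 0.793.

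**Simulation** (400,000 draws, normal approximation), power for enhanced versus standard on MoCA:

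| Setting | Bonferroni | Holm | Gain (points) |
|---|---|---|---|
| SD of change 3.5, dual-task effects equal to MoCA's | 64% | 78-79% | 14-15 |
| SD of change 3.5, dual-task effects half as large | 64% | 72-73% | 8-9 |
| SD of change 3.5, no dual-task effect | 64% | 68% | 4 |
| SD of change 3.5 × √(2 × (1 − 0.7)) = 2.71, equal effects | 88% | 95-96% | about 7 |

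In the first setting, power for all four contrasts together rises from 41-49% to 66-70%. With the plan's rounded effect sizes (0.4 and 0.8), 57% becomes 72-73%. Under the global null, simulated family-wise error is the same for both procedures, 4.3-4.7%.

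**Agreement with the intervals.** Bonferroni rejects at 0.0125 exactly when the 98.75% interval excludes zero. Every extra Holm rejection therefore has p ≥ 0.0125 and an interval that includes zero. Take equal effects and independent outcomes, with the stretching contrasts rejected. The chance of at least one such contrast is the sum of two parts:
- One enhanced-versus-standard p-value below 0.0125 and the other between 0.0125 and 0.05: 2 × 0.641 × (0.816 − 0.641) = 0.224.
- The smaller of the two between 0.0125 and 0.025: 0.091² + 2 × 0.091 × 0.268 = 0.057, where 0.091 = 0.732 − 0.641 and 0.268 = 1 − 0.732.

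The total is 28%. Simulation gives 25-28% for outcome correlations from 0 to 0.5.

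**The case against.** **Bonferroni is valid, pre-specified and consistently stated.** This stands. A reader might infer that the plan contains an error or fails to control its error rate. It does neither. Holm is one of several valid alternatives, and the case for it is efficiency.

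**Bonferroni gives simple simultaneous intervals that always match the test, and Holm breaks that match.** This stands too, and it is the real cost. It would be tempting to call the mismatch a borderline rarity. Under the equal-effect assumptions at least one such contrast appears in about a quarter of trials, and the plan makes mean differences with 98.75% intervals its reported result.

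**The gain rests on inputs the plan does not settle.** Correct. With no dual-task SD, 15 points cannot be taken as the loss; it belongs to the equal-effect setting. It is also not a strict maximum: if the other three contrasts were all near-certain rejections, the gain would be 17.5 points (64.1% to 81.6%). Nor is 4 a strict minimum. With the 2.71 SD and no dual-task effect, the contrast is in effect tested at 0.0167, where power is 90.3% against 88.4%, a gain of about 2 points.

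**The low starting power has another cause.** Power was calculated as "detectable with at least 80% power using a 2-sided 0.05-level test", while testing is at 0.0125. On the SD 3.5 reading that moves 81.6% to 64.1%. It is a separate matter, and Holm does not fully close it.

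A reader might also infer that enhanced versus standard is tested more strictly than the other contrasts. All four share the same 0.0125. The interaction gate applies to both procedures alike; with a 3-point planned effect it should nearly always open, though this was not simulated.

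**Conclusion.** The point holds as a cheap improvement. Fixed testing at 0.0125 is sound, but Holm dominates it for the accept/reject decision at the same 5% family-wise error. Across the four settings in the table, the gain for enhanced versus standard on MoCA is about 4 to 15 points. Its size depends on whether 3.5 is the SD of change (the reading that best reproduces the stated power) and on the unknown standardized dual-task effects. On the 0.7-correlation reading, power already exceeds 80% under Bonferroni, so the gain is useful but not needed to reach the target.

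The documents do not support applying Holm to results already in hand. Both carry a September 2024 update date and cite a results publication from October 2023. A more liberal rule adopted after results are known would be a post hoc change to the primary decision.

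**What to change.** In the Synopsis (Statistical analysis) and in the significance-level paragraph for the co-primary endpoints in both documents, replace the fixed 0.0125 with Holm's procedure: order the four p-values, compare them with 0.0125, 0.0167, 0.025 and 0.05, and stop at the first failure. State that the Holm decision governs the claim. Keep the 98.75% intervals, labelled as conservative simultaneous intervals, and say in advance that a contrast can be significant by Holm while its interval includes zero, so that the report explains it.

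Apply this only to analyses not yet done. The 48-week comparisons of the primary outcomes, which reuse the primary strategy, qualify only if they are still unanalysed. For results already analysed, keep the Bonferroni rule; Holm may appear there only as a labelled supplementary analysis.

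The change needs wording only, with no new data, visits or participants. The cost is the loss of one-to-one agreement between test and interval.

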With the longitudinal data, we will test the hypothesis that the rate of improvement over time in the mean CDR-SB score, at 24-week post-intervention follow-up, will be greater in the cognitively enhanced tai ji quan group compared with the other two exercise groups. To test this hypothesis, we will use the latent growth curve modeling approach,³⁵ with maximum-likelihood estimation, analyzing the rate of change in the mean CDR-SB score defined by the four measurement time points: baseline, 16 weeks (mid intervention assessment), 24 weeks (end of intervention assessment), and 48 weeks (24 weeks post intervention follow-up).

Accordingly, we will operationalize our basic growth curve model with two latent growth factors: Intercept (defining the initial level of CDR-SB – baseline) and Slope (defining the rate of change over the course of the 48-week study period), with each factor being defined by the four time-specific CDR-SB

measures. A schematic representation of the planned latent growth model to be evaluated for each intervention group is shown in Figure 1. The factor loadings for the Intercept factor will be fixed with a constant value of 1 for all measurement points whereas the loadings for the Slope factor, defining the rate of change over time, will be fixed at 0 for CDR-SB at baseline, 1 for CDR-SB at 16 weeks, 2 for CDR-SB at 24 weeks, and * for CDR-SB at 48 weeks (where * indicating an undefined, free estimate at 48 weeks). All other model parameters to be estimated include latent Intercept mean and its variance, latent Slope mean and its variance, the correlation between Intercept and Slope (covariance), and error variance for each of the four time-specific measurements (shown as E's). The model estimation will include all available data derived from the trial, hence, an intent-to-treat approach.

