The model estimation of change in CDR-SB will involve two steps. First, we will estimate an unconditional latent growth model (i.e., without the group predictor [e.g., cognitively enhanced tai ji quan group vs standard tai ji quan group]). This unconditional growth curve model allows us to examine the overall pattern of change in the CDR-SB score over time. Next, a group predictor (as a binary variable [1=cognitively enhanced tai ji quan group and 2=standard tai ji quan group]) is added to the model parameterization. By regressing the Slope factor on to the predictor of the group variable, this model will examine the pre-specified intervention effect of the cognitively enhanced tai ji quan training, compared with each of other two active groups, individually, on the rate of change in cognitive functioning trajectories. The schematic representation of this second latent growth model with the group, as a predictor, is shown Figure 2 (next page). For reporting purposes, we will present (a) latent slope mean for each group and (b) the regression coefficient relating group and the latent slope (with 95% CI). A negative slope mean for CDR-SB will indicate an improvement in cognitive functioning and, therefore, a lowering of the disease progression, whereas a positive mean slope will indicate deterioration in cognitive functioning.

A statistically significant regression coefficient indicates the difference in the rate of CDR-SB progression. All tests and CIs will be 2-sided, and statistical significance will be defined as a P value of <0.05. The planned statistical analyses on change in CDR-SB will be performed in *Mplus* statistical software version 8.2 (Muthén & Muthén).

[figure not shown]

Figure 1. Latent growth curve model (intercept and slope) of change in CDR-SB over the 48-week study period

Note:

Intercept: defines the CDR-SB score at baseline

[figure not shown]
Slope: defines change or progression in the CDR-SB score from baseline to 48 weeks

*indicating an undefined, freely estimated loading at 48 weeks

Values in the squared box indicates observed value at each measurement time point

E1 through E4 represent measurement error at each measurement time point

Figure 2. Latent growth (intercept and slope) model for examining intervention effect on CDR-SB over the 48-week study period

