Intervention fidelity will focus primarily on issues such as (a) interventionist qualifications and training, (b) teaching quality of the individual forms/movements or routine in each session, (c) exercise intensity and consistency in training dosage across different sites, and (d) weekly class attendance checking and monitoring. The evaluation will be conducted monthly by either an authorized research team member or an instructor, per guidelines specified in an established fidelity checklist. ¹⁰ In evaluating the item in (b), high intervention fidelity will be considered achieved if at least 95% of the mandatory components (overall completion of pre-specified activities, quality of verbal and visual instructions, emphasis of core training points, session completion time) are fully or partially delivered in each session. Deviations related to intervention delivery protocol will be captured on a protocol deviation form and be entered into a project database for evaluation by the research staff and Principal Investigator. Prompt action will be taken by the Principal Investigator to remedy any problems and deviations identified.

Data completeness and quality control

Data completion refers to the study measurement ascertainment status from all enrolled study participants. The project strives to collect study outcome measures on every participant at each scheduled time point (baseline, 4 months, 6 months, and 12 months), regardless of his/her intervention participation status. As specified in the protocol for the study, we have planned an overall study retention rate of 85% (i.e., having primary and secondary outcome measures available on 85% of the enrolled participants and their informants). To accomplish this goal, planned measures will be taken to ensure that as many participants as possible, including dropouts, attend each scheduled in-person assessment visit at our research facilities. Our proactive methods will include frequent telephone and e-mail contacts with subjects who miss scheduled data assessment appointments. The planned completion of data ascertainment at each follow-up time point is described in the Table 2 below.

Table 2. Projected completion of data ascertainment on study outcome measures at each measurement time point

Measure\Time point	4 months	6 months	12 months
Primary	95%	90%	85%
Secondary	95%	90%	85%
Tertiary	95%	90%	85%

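### The CDR-SB growth model codes weeks 0, 16 and 24 as 0, 1, 2, so its slope means and group coefficient are not the rates that the plan calls them

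*Protocol*

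**What the plan says.** The text is the same in the protocol's Statistical Analysis Plan and in the separate SAP, under *Analyses on examining intervention durability at 48-week follow-up*.

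- **Visit times.** CDR-SB is measured at "baseline, 16 weeks (mid intervention assessment), 24 weeks (end of intervention assessment), and 48 weeks (24 weeks post intervention follow-up"). *Data completeness and quality control* gives the same schedule in months: "at each scheduled time point (baseline, 4 months, 6 months, and 12 months").
- **Loadings.** The Slope loadings "will be fixed at 0 for CDR-SB at baseline, 1 for CDR-SB at 16 weeks, 2 for CDR-SB at 24 weeks". The fourth is left open ("where * indicating an undefined, free estimate at 48 weeks").
- **Meaning given to the Slope.** The text describes it as "defining the rate of change over the course of the 48-week study period". The note to Figure 1 says that it "defines change or progression in the CDR-SB score from baseline to 48 weeks".
- **Reporting.** The plan will present the slope mean in each group and the coefficient of the Slope on group with a 95% CI. It reads the latter as follows: "A statistically significant regression coefficient indicates the difference in the rate of CDR-SB progression".

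No section names a time unit for the Slope or gives a reason for equal steps.

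**The concern.** A growth factor is a rate only if its loadings are proportional to time. Here one coded step lasts 16 weeks and the next lasts 8, so a coefficient per step has no constant unit. The model also imposes a shape on both arms and on the difference between them: the change after week 16 runs twice as fast per week as the change before it.

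CDR-SB is the key secondary outcome. This model carries the part of the secondary hypothesis about slowing progression to dementia, and the durability section exempts CDR-SB from the general strategy in its favour. A reader who takes the published coefficient as points per 16 weeks, or divides it by 16 to get a weekly rate, would be misled about the size of the effect.

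**Working it through.** **1. Loadings against elapsed time**

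| | Week 0 | Week 16 | Week 24 | Week 48 |
|---|---|---|---|---|
| Plan | 0 | 1 | 2 | free |
| Weeks / 16 | 0 | 1 | 1.5 | 3 |
| Months / 4 | 0 | 1 | 1.5 | 3 |

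The plan's 0, 1, 2 is reproduced only as visit number. With Slope value S, the modelled change is S over weeks 0–16 and S again over weeks 16–24. The weekly rate is S/16 = 0.0625 S, then S/8 = 0.125 S. By its own loadings, S is the change to week 16 and half the change to week 24. It is neither a 48-week rate nor the change to week 48.

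**2. Size of the effect if change is linear in weeks**

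The planned model (Slope regressed on group, Intercept not, week 48 free) was fitted at population level by maximum likelihood to exactly linear trajectories.

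- From the documents: the visit times, the loadings, and 267 evaluable participants (*Power estimation for primary outcomes*). That is 267/3 = 89 per arm, or 178 per pairwise model.
- Assumed: 48-week changes of −0.60 and −0.15 points; baseline true-score SD 1.0; error variance 0.1 to 0.6; slope SD 0.15 to 0.30 per 16 weeks.
- True group difference: 0.60 − 0.15 = 0.45 over 48 weeks, which is 0.45/3 = 0.150 per 16 weeks and 0.150 × 1.5 = 0.225 at week 24.

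Results under 0, 1, 2, free (b is the group coefficient):

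| Error variance | Slope SD | b | b / 0.150 | 2b (true 0.225) | Week-48 loading | Power, planned coding | Power, 0, 1, 1.5 |
|---|---|---|---|---|---|---|---|
| 0.1 | 0.15 | 0.1110 | 74% | 0.222 | 3.94 | 0.997 | 0.997 |
| 0.1 | 0.30 | 0.1051 | 70% | 0.210 | 4.11 | 0.839 | 0.844 |
| 0.3 | 0.15 | 0.1129 | 75% | 0.226 | 3.89 | 0.934 | 0.935 |
| 0.3 | 0.30 | 0.1107 | 74% | 0.221 | 3.96 | 0.730 | 0.733 |
| 0.6 | 0.15 | 0.1139 | 76% | 0.228 | 3.88 | 0.786 | 0.789 |
| 0.6 | 0.30 | 0.1134 | 76% | 0.227 | 3.89 | 0.610 | 0.612 |

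With 0, 1, 1.5, free, the coefficient was 0.150 and the week-48 loading 3.0 in all six cases.

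**3. What the table shows**

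- *Coefficient per 16 weeks, and week-16 difference.* Both equal b, because the week-16 loading is 1. They are 24% to 30% too small.
- *Week-24 difference.* The model implies 2b = 0.210 to 0.228 against 0.225. The largest error is (0.225 − 0.210)/0.225 = 7%.
- *Week-48 loading.* It settles at 3.88 to 4.11 instead of 3.0. The free loading cannot repair the spacing, because the three earlier loadings are fixed.
- *Test.* Power differs by at most 0.005. If the arms share one trajectory, the coefficient is zero under either coding, so the test still addresses the right null hypothesis.
- *Detectability.* The expected misfit chi-square at N = 178 is 0.3 to 6.0, so a fit statistic may not reveal the problem.

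**The case against.** Four arguments can be made for leaving the plan alone.

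1. **CDR-SB does not depend on this slope alone.** This is correct. *Secondary and tertiary outcome analyses* applies the Group by Time mixed model to every continuous outcome in Table 1, CDR-SB included, with between-group differences at 24 weeks. The exception for CDR-SB covers only the 48-week analysis. A reader might infer that the slope is the sole planned longitudinal estimate for CDR-SB; the documents do not support that.

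2. **The shortfall depends on how the coefficient is read.** This is also correct. Doubled, the coefficient gives nearly the right week-24 difference. But the plan calls the coefficient a difference in rate and names no unit, so nothing tells a reader to double it.

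3. **Linear change is not the plan's claim, and acceleration is plausible.** The enhanced programme learns forms in weeks 1–15 and integrates cognitive tasks in weeks 16–24. With an assumed difference of −0.125 at week 16 and −0.50 at weeks 24 and 48, a refit (intercept SD 1, slope SD 0.15 to 0.30 per 16 weeks, error variance 0.1 to 0.4) gave −0.22 to −0.23 and −0.45 to −0.47 at weeks 16 and 24 under 0, 1, 2. Under 0, 1, 1.5 it gave −0.26 to −0.28 and −0.39 to −0.41, which is further from the truth at both visits. The exact values depend on the path assumed for the comparator arm; the ordering is what matters. So proportional loadings are not always the better fit. Still, the plan does not offer this as its reason, the same loadings apply to arms without cognitive integration, and the week-15 sample session already contains integrative tasks. If acceleration is intended, the factor is not a rate.

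4. **The inference is spared.** It is, as the power figures show. A reader might infer that the P value or type I error is invalid; neither the documents nor the calculation supports that. What is affected is the slope means, the coefficient and its CI, which the plan undertakes to report.

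**Conclusion.** Wrong as written, and limited to the estimates of one secondary analysis. That the loadings follow visit order rather than time, and so do not define a rate, comes from the documents alone and needs no assumption.

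The size of the error does need one. The shortfall of 24% to 30% holds if change is linear in weeks and the coefficient is read per 16 weeks. The variances and effects behind it are illustrative, because the documents give none for CDR-SB. The week-24 difference implied by the model, the significance test, the 24-week CDR-SB mixed model and the co-primary analyses give no cause for concern on this point.

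**What to change.** Choose one of two forms and state it in the durability section of both documents.

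- **If change to week 24 is taken as linear:** set the loadings proportional to weeks, either 0, 1, 1.5 (Slope is change per 16 weeks) or 0, 0.667, 1 (Slope is change to week 24, and dividing by 24 gives a weekly rate). Week 48 stays free. State the unit beside the slope means, the coefficient and the CI.
- **If it is not:** fix baseline at 0 and week 24 at 1, free week 16 as well as week 48, report the Slope as change to week 24, and do not call it a rate.

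Under either form, correct the two descriptions of the Slope as a 48-week quantity. While week 48 is free, the fixed loadings tie the Slope's unit to the first 24 weeks.

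The cost is a line or two of SAP wording and one line of Mplus code, with no new data. If the model has already been run, it should be rerun and the slope estimates reported in the stated unit.
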